4.2 Scientific rationale for study design

Table 4-1 Rationale for study design

Study Design Aspect	Rationale
Open-label	Design is to assess safety, and all participants will receive active treatment
Eligibility	All participants who completed CLTP001A12201 treatment period and have not met study treatment discontinuation criteria are eligible to enroll. At the time of enrollment, efficacy of LTP001 is unknown, therefore all participants who may benefit can enroll in this extension protocol.
Planned off-site procedures	Off-site procedures are planned in this study to minimize burden on participants, and offer them increased flexibility to participate in the study from an off-site location. This has the potential to broaden access to clinical trials for both participants and investigators. The hybrid approach will allow participants to maintain contact with investigator, both in-person during clinic visits and through the telemedicine platform during off-site participation.

4.3 Justification for dose

LTP001 will be administered once daily CCI at a dose level of ■ mg. This is the same posology as used in the parent study, CLTP001A12201.

In healthy participants, this dose has been shown to be well tolerated at single and multiple dose administrations. CCI

■ this dose level should be adequate and provide full efficacy. Further details are provided in the Investigator's Brochure.

4.3.1 Rationale for choice of background therapy

Participants will remain on the same background therapy as in the parent study, CLTP001A12201, (for details please refer to [Section 6](#)) and should not be changed during the extension study. Typically, if there is a deterioration of the participant's PAH condition requiring an escalation of concomitant PAH-specific treatment, the participant should be discontinued from the study treatment (for detailed study discontinuation criteria see [Section 7.2](#)) and subsequently return for the EOT assessments. However, if the investigator thinks that the participant should remain on study drug the Novartis medical monitor should be contacted to discuss the change of concomitant PAH medication and the reasons why it is thought to be beneficial for the participant to stay on study drug.

4.4 Rationale for choice of control drugs (comparator/placebo) or combination drugs

This is an open label extension study, where all participants are planned to receive active treatment with LTP001. No control treatment is planned during this study. This allows all participants to potentially benefit from treatment, if LTP001 yields clinical benefit in PAH.

4.5 Rationale for public health emergency mitigation procedures

In addition to the planned off-site procedures, in the event of a public health emergency as declared by local or regional authorities (i.e. pandemic, epidemic or natural disaster), mitigation procedures to ensure participant safety and trial integrity may be implemented.

If allowable by a local health authority and depending on operational capabilities, phone calls, virtual contacts (e.g. tele consult) or additional visits by OHPs to the participant's home can replace on-site study visits (in addition to the already planned off-site visits), for the duration of the disruption until it is safe for the participant to visit the site again.

Notification of the public health emergency should be discussed with Novartis prior to implementation of mitigation procedures and permitted/approved by local or regional health authorities and ethics committees as appropriate.

4.6 Purpose and timing of interim analyses/design adaptations

There are no prospectively planned interim analyses. Interim analyses may be conducted to support decision-making concerning the current clinical study, the sponsor's clinical development projects in general, to provide regular safety updates or in case of any safety concerns.

4.7 End of study definition

The end of the study is defined as the date of the last visit of the last participant in the study.

Study completion is defined as when the last participant finishes their last study visit and any repeat assessments associated with this visit have been documented and followed-up appropriately by the Investigator.

5 Study population

The study population will be comprised of male and female participants with pulmonary arterial hypertension.

Approximately 40 participants are expected to complete parent study CLTP001A12201 and meet the study entry criteria for this open label extension study.

The investigator must ensure that all participants being considered for the study meet the following eligibility criteria. No additional criteria should be applied by the investigator in order that the study population will be representative of all eligible participants.

5.1 Inclusion criteria

Participants eligible for inclusion in this study must meet **all** of the following criteria:

1. Written informed consent must be obtained before any assessment is performed.
2. Participant is currently completing the Novartis-sponsored study CLTP001A12201 in PAH and completed key efficacy and safety procedures up to the end of treatment of the core study, without meeting discontinuation criteria in the core study.
3. Willingness and ability to comply with scheduled visits, treatment plans and any other study procedures.
5. In the opinion of the Investigator would benefit from LTP001 treatment.

5.2 Exclusion criteria

Participants meeting any of the following criteria are not eligible for inclusion in this study.

1. History of hypersensitivity to the study treatment.
2. Sexually active males not committing to condom use precautions: sexually active males must use a condom during intercourse while taking drug and for 24 hours after stopping study medication and should not father a child in this period nor donate sperm. A condom is required to be used also by vasectomized men in order to prevent delivery of the drug via seminal fluid.
3. Required or planned transplant or heart/lung surgery.
4. Women of child-bearing potential, defined as all women physiologically capable of becoming pregnant, **unless** they are using highly effective methods of contraception while taking study treatment and until EOT visit (2 weeks post-last treatment). Highly effective contraception methods include:
 - Total abstinence (when this is in line with the preferred and usual lifestyle of the participant. Periodic abstinence (e.g. calendar, ovulation, symptothermal, post-ovulation methods) and withdrawal are not acceptable methods of contraception.

- Female sterilization (have had surgical bilateral oophorectomy with or without hysterectomy), total hysterectomy, or bilateral tubal ligation at least six weeks before taking study treatment. In case of oophorectomy alone, only when the reproductive status of the woman has been confirmed by follow up hormone level assessment.
- Male sterilization (at least 6 months prior to screening). For female participants on the study, the vasectomized male partner should be the sole partner for that participant
- Use of oral, estrogen and progesterone, injected, or implanted hormonal methods of contraception or placement of an intrauterine device (IUD) or intrauterine system (IUS), or other forms of hormonal contraception that have comparable efficacy (failure rate < 1%), for example hormone vaginal ring or transdermal hormone contraception.

In case of use of oral contraception women should have been stable on the same pill for a minimum of 3 months before taking study treatment.

Women are considered post-menopausal if they have had 12 months of natural (spontaneous) amenorrhea with an appropriate clinical profile (e.g. age appropriate history of vasomotor symptoms). Women are considered not of child-bearing potential if they are post-menopausal or have had surgical bilateral oophorectomy (with or without hysterectomy) or total hysterectomy at least six weeks ago. In the case of oophorectomy alone, only when the reproductive status of the woman has been confirmed by follow up hormone level assessment is she considered not of child bearing potential.

5. Pregnant or nursing (lactating) women, where pregnancy is defined as the state of a female after conception and until the termination of gestation, confirmed by a positive hCG laboratory test.
6. Acute or chronic impairment (other than dyspnea), which would limit the ability to comply with study requirements, including interference with physical activity or execution of study procedures such as 6MWT (e.g., angina pectoris, claudication, musculoskeletal disorder, need for walking aids).
7. Permanent discontinuation of Novartis drug in the core efficacy study due to toxicity or disease progression despite active treatment, non-compliance to study procedures, withdrawal of consent or any other reason.

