- The treatment duration will be up to 52 weeks.

- The visit frequency will include visits at weeks 1, 5, 13, 26, 39, 52, and 56.

Treatment of interest

The treatment of interest is LTP001 [REDACTED] mg daily on top of allowed standard of care treatment for PAH. The dose of the allowed concomitant medication should remain stable during the trial.

Number of Participants:

The study population is comprised of male and female adults with PAH. A total of approximately 40 participants are planned to complete the parent study CLTP001A12201 and meet the study entry criteria for this open label extension study.

Key Inclusion criteria:

- Written informed consent must be obtained before any assessment is performed.
- Participant is currently completing the Novartis-sponsored study CLTP001A12201 in PAH and completed key efficacy and safety procedures up to the end of treatment of the parent study, without meeting discontinuation criteria in the parent study.
- Willingness and ability to comply with scheduled visits, treatment plans and any other study procedures.
- In the opinion of the Investigator the participant would benefit from LTP001 treatment.

Key Exclusion criteria:

- History of hypersensitivity to the study treatment.
- Required or planned transplant or heart/lung surgery.
- Acute or chronic impairment (other than dyspnea), which would limit the ability to comply with study requirements, including interference with physical activity or execution of study procedures such as 6MWT (e.g., angina pectoris, claudication, musculoskeletal disorder, need for walking aids).
- Permanent discontinuation of Novartis drug in the parent study due to toxicity or disease progression, non-compliance to study procedures, withdrawal of consent or any other reason.

Treatment Groups:

Active treatment: LTP001 administered as [REDACTED] mg once daily CCI [REDACTED] (CCI [REDACTED]). Investigational study treatment dose adjustments and/or interruptions are not permitted.

Data Monitoring/Other Committee:

Yes; the DMC instituted for the parent study will also receive data from this extension study (see [Section 10.1.4 Committees Structure](#)).

Key words:

Pulmonary arterial hypertension, pulmonary vascular resistance, 6 minute walk distance, time to clinical worsening, SMURF1 inhibitor, echocardiography, patient reported outcomes

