1.2 Schema**Figure 1-1 Study Schema****1.3 Assessment Schedule**

The Assessment Schedule lists all of the assessments when they are performed. All data obtained from these assessments must be supported in the participant's source documentation. The "X" in the table denotes the assessments to be recorded in the clinical database or received electronically from a vendor. The "S" in the table denotes the assessments that are only in the participant's source documentation and do not need to be recorded in the clinical database.

Participants should be seen for all visits/assessments as outlined in the Assessment Schedule or as close to the designated day/time as possible. Missed or rescheduled visits should not lead to automatic discontinuation.

Participants who discontinue from study treatment are to complete the end of treatment visit as soon as possible, and attend the follow-up visits as indicated in the Assessment Schedule.

Participants who discontinue from study should be scheduled for a final evaluation visit if they agree, as soon as possible, at which time all of the assessments listed for the final visit will be performed. At this final visit, all dispensed investigational product should be reconciled, and the adverse events and concomitant medications not previously reported must be recorded on the CRF.

PRO measures must be completed before any assessments are performed at any given visit.

As per [Section 4.5](#), during a public health emergency as declared by local or regional authorities (i.e. pandemic, epidemic or natural disaster that limits or prevents on-site study visits), alternative methods of providing continuing care may be implemented by the Investigator as the situation dictates. If allowable by a local health authority, national and local regulations and depending on operational capabilities, phone calls, virtual contacts (e.g. tele consultation) or visits by site staff/ off-site healthcare professional(s) staff to the participant's home, can replace certain protocol assessments, for the duration of the disruption until it is safe for the participant to visit the site again. If the Investigator delegates tasks to an off-site healthcare professional, the Investigator must ensure the individual(s) is/are qualified and appropriately trained to perform assigned duties. The Investigator must oversee their conduct and remain responsible for the evaluation of the data collected.

Table 1-2 Assessment Schedule

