Period	Baseline		Extension Treatment Up To Month 12							
Visit Name	Transition Period		Treatment						EOT	Post Study Safety Contact
Visit Numbers ¹	1 ²	100 ²	110		120		130	140	150	
Days	-14 to -1	1	29 ±7	57 ±10	85 ±10	113 ±10	176 ±10	267 ±10	358 ±10	Last treatment +30 -0 +7
Weeks	-2 to -1	1	5 ±1	9 ±2	13 ±2	17 ±2	26 ±2	39 ±2	52 ±2	57 -0 +1
Informed consent ^{3,4}	X									
Inclusion / Exclusion criteria	X									
Physical Examination			S	S ⁸	S	S ⁸	S	S	S	
Body Weight			X	X ⁸	X	X ⁸	X	X	X	
Body Temperature			X	X ⁸	X	X ⁸	X	X	X	
Blood Pressure and Pulse Rate			X	X ⁸	X	X ⁸	X	X	X	
Electrocardiogram (ECG)			X	X ⁸	X	X ⁸	X	X	X	
Dose administration ⁵	X	X	X ⁸	X	X ⁸	X	X	X	X	
Drug dispensation	X	X		X			X	X		
Collect study medication/perform drug accountability ⁵			X	X ⁸	X	X ⁸	X	X	X	
Urinalysis			X	X ⁸	X	X ⁸	X	X	X	
Pregnancy and assessments of fertility			S	S ⁸	S	S ⁸	S	S	S	
Hematology			X	X ⁸	X	X ⁸	X	X	X	
Clinical Chemistry			X	X ⁸	X	X ⁸	X	X	X	

Period	Baseline		Extension Treatment Up To Month 12								
Visit Name	Transition Period		Treatment						EOT	Post Study Safety Contact	
Visit Numbers ¹	1 ²	100 ²	110		120		130	140	150		
Days	-14 to -1	1	29 ±7	57 ±10	85 ±10	113 ±10	176 ±10	267 ±10	358 ±10	Last treatment +30 -0 +7	
Weeks	-2 to -1	1	5 ±1	9 ±2	13 ±2	17 ±2	26 ±2	39 ±2	52 ±2	57 -0 +1	
Coagulation Panel			X	X ⁸	X	X ⁸	X	X	X		
NT-proBNP				X		X		X	X		
emPHasis-10 and PAH-SYMPACT ⁶			X ⁷		X ⁷		X ⁷	X ⁷	X ⁷		
Right Heart Catheterization ⁴							X				
6-Minute Walk Test ⁴							X		X		
Echocardiogram ⁴							X		X		
Concomitant Medications/Adverse Events								X			
Study completion information									X		

Period	Baseline		Extension Treatment Up To Month 12							
Visit Name	Transition Period		Treatment					EOT	Post Study Safety Contact	
Visit Numbers ¹	1 ²	100 ²	110		120		130	140	150	
Days	-14 to -1	1	29 ±7	57 ±10	85 ±10	113 ±10	176 ±10	267 ±10	358 ±10	Last treatment +30 -0 +7
Weeks	-2 to -1	1	5 ±1	9 ±2	13 ±2	17 ±2	26 ±2	39 ±2	52 ±2	57 -0 +1
Safety Follow up Call			S		S					S

^X Assessment to be recorded in the clinical database or received electronically from a vendor

^S Assessment to be recorded in the source documentation only

¹ Visit structure given for internal programming purpose only

² Baseline and Day 1 can be on the same day or within a 14-day transition period

³ CCI

⁴ Assessment must be performed onsite. All other assessments may be performed at an off-site location.

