2.3 Benefit/Risk assessment

Potential risks are based on the mechanism of action, the nonclinical toxicology data, and the safety data from the FIH study.

LTP001 is the first SMURF1 inhibitor to be developed. Based on current understanding of SMURF1 biology, there are no concerns directly related to this mechanism of action; and, because LTP001 is first-in-class, there are no previously identified clinical safety risks (i.e., no known class effects).

Preclinical data

CCI

CCI

Clinical data

Single doses of LTP001 CCI mg, CCI mg, CCI mg, CCI mg, CCI mg and CCI mg were well tolerated and did not show safety signals for LTP001 in the first in human study.

Multiple doses of LTP001 CCI mg, CCI mg, CCI mg, CCI mg and CCI mg once daily and CCI mg bid were well tolerated. CCI

CCI , clinical laboratory assessments, ECGs, and vital signs did not show significant abnormalities. CCI

The risk to participants in this trial will be minimized by adherence to the eligibility criteria, close clinical monitoring, regular safety data reviews, and pre-specified rules for automatically stopping the study should unanticipated safety issues suddenly arise.

No reproductive toxicology studies have been performed for LTP001. Women of child-bearing potential will be only enrolled if they use highly effective contraception methods.

Additional details about potential risks of LTP001 can be found in the Investigator's Brochure.

Procedural risks

Cardiac catheterization is a safe procedure when performed by an experienced medical team. However, there may be some possible risks such as bleeding, infection, and blood clots. A heart attack or a stroke can happen in very rare situations. Right heart catheterization (RHC) is regularly employed to monitor the course of PAH. RHC may be performed without radiation but for optimal placement of the catheter, the investigator can employ x-ray to double-check the positioning of the catheter when measurements are made. RHC does not employ contrast media. RHC is required to calculate PVR. PVR was the primary efficacy assessment of the

parent study, CLTP001A12201, and is performed at Week 26 in the current study, which allows the assessment of the 1-year effect of LTP001 of those participants who received LTP001 already in the parent study, and the 6-month effect on PVR of those who received placebo in the parent study. This data is considered very important to assess the long-term effect of LTP001 on PVR in patients with PAH.

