The safety and efficacy of LTP001 will be checked at the following visits: Weeks 5, 13, 26, 39 and 52, as specified in the Assessment Schedule. Safety and tolerability assessments will take place at each visit. RHC will be performed at week 26, 6MWT and echocardiography will be assessed at Weeks 26 and 52. PAH-SYMPACT and emPHasis-10 will be collected for 7 days intervals with the seventh day of collection occurring within the allotted visit window for all Treatment visits (Weeks 5, 13, 26, 39 and 52). Participants will have safety follow-up phone calls at Weeks 9 and 17, and may be invited for safety assessment at site if deemed necessary. The PI may exercise their discretion in which safety assessments are required at these optional safety follow-up visits. Following the end of treatment period, participants will have one safety follow-up phone call approximately 30 days after the end of treatment visit at Week 52. The duration of the extension study is currently restricted to 52 weeks, but the study may be prolonged (via an amendment to the protocol) if the LTP001 development program in PAH continues and the benefit/risk assessment remains favorable for the patient population studied. The safety and efficacy profile of LTP001 that is observed in this extension study as well as the parent study, CLTP001A12201, will determine continuation of the extension study.

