6.2.3 Instruction for prescribing and taking study treatment

LTP001 should be taken daily at approximately the same time each day **CCI**. On clinic visit days, the participant should take LTP001 during the clinic visit when instructed by the study staff. 6MWT and RHC assessment should be executed at approximately the same time after drug administration each time (tolerance window +/- 1 hour).

CCI

If vomiting occurs during the course of treatment, participants should not take the study treatment LTP001 again before the next scheduled dose.

Participants should be instructed not to make up missed doses. A missed dose is defined as a case when the full dose is not taken within 12 hours after the approximate time of the usual daily dosing. That day's dose should be omitted and the participant should continue treatment with the next scheduled dose.

The first day the participant is seen by an off-site health professional during the visit window, or the first day of a visit to the clinical site should be the dose recorded in the Dosage Form eCRF.

Novartis will provide the site with a participant study card to hand over to all study participants, which will state that the participant is participating in a clinical study and is receiving an investigational product. This participant study card will also include the contact information of the Study Doctor/Investigative Site. Designated study staff will instruct study participants to present this card to a medical care provider if they have any medical issues during the course of the study.

All kits of study treatment assigned by the IRT will be recorded in the IRT system.

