2.1.1 General definitions

Investigational treatment will be LTP001.

Date of first administration of study treatment (Day 1) will be defined as the date of the first actual administration of LTP001.

Date of last administration of study treatment will be defined as the date of the last actual administration of LTP001.

Two *Baselines* will be defined as the following:

Baseline of the Parent study: the Day 1 assessment of study LTP001A12201. If this datum is not available, the last pre-dosing assessment will be considered.

Baseline of the Extension study: Week 25 visit from LTP001A12201. If this datum is not available, the last pre-dosing assessment for this study (LTP001A12201E1) will be considered. *Study day* will be defined as the number of days since the date of first dose of study treatment (LTP001 or placebo). The date of first dose of study treatment will be defined as *Day 1* and the day prior to first dose of will be defined as *Day -1*. Therefore, for a particular date, study day will be calculated as follows:

for dates on or after the date of first dose of study treatment,

Study day = Assessment date – Date of first dose administration + 1

The on-treatment period lasts from the date of first administration of study treatment to the End of Study (EOS) visit or the date of last randomized dose if EOS visit is not available. The EOS visit is a follow-up visit that is approximately 30 days after the date of the last actual administration of investigational treatment. For participants who will be enrolled into the open label extension (OLE) study, their EOS visits will be skipped.

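### Exclusion criterion 4 gives women two different end dates for contraception: the EOT visit (about 0 days after the last dose) and 2 weeks after the last dose

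*Protocol*

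**What the plan says.** Criterion 4 of Protocol Section 5.2 admits women of child-bearing potential only if "they are using highly effective methods of contraception while taking study treatment and until EOT visit (2 weeks post-last treatment"). One end point is named in two ways: as a visit, and as an interval after the last dose.

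Other parts of the plan fix when that visit happens:

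- Protocol 1.1 Summary: "The treatment duration will be up to 52 weeks".
- Protocol Table 1-2: the EOT visit is at Week 52 ±2, Day 358 ±10. The post-study safety contact is at "Last treatment +30 -0 +7" days, in a column labelled Week 57.
- Protocol 4.1: "participants will have one safety follow-up phone call approximately 30 days after the end of treatment visit at Week 52".
- Protocol 1.3, for early stoppers: "Participants who discontinue from study treatment are to complete the end of treatment visit as soon as possible".
- Protocol 6.2.3, as a general dosing instruction: "On clinic visit days, the participant should take LTP001 during the clinic visit when instructed by the study staff".
- SAP 2.1.1: "The EOS visit is a follow-up visit that is approximately 30 days after the date of the last actual administration of investigational treatment".

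On the reason for the precaution, Protocol 2.3 states: "No reproductive toxicology studies have been performed for LTP001". The same section sends the reader back to the exclusion criteria for the contraception rules. Section 8.4.3 sets an end time only for men (24 hours after stopping), and Section 10.1.2 refers to the requirements without giving a duration.

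**The concern.** If EOT takes place at about the last dose, the two halves of the criterion name different days, and nothing tells a site which half governs. A site that works from the visit calendar could tell a woman that contraception may stop on the day of her last tablet. A site that works from the parenthesis would keep it going for two more weeks.

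This is the only rule in the protocol on how long women must continue contraception after dosing, and it applies to a drug without reproductive toxicology data. In Table 1-2 the pregnancy-test row ends at EOT and the later contact is a phone call, so no scheduled test covers the disputed days. Section 8.6.4 requires any pregnancy that becomes known to be reported within 24 hours. The weakness is therefore in prevention and not in reporting.

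**Working it through.** **Inputs.** EOT on Day 358 ±10 (Table 1-2). Treatment up to 52 weeks, 52 × 7 = 364 days (Section 1.1). Safety contact at last treatment +30 to +37 days (Table 1-2), also about 30 days after EOT (Section 4.1), labelled Week 56 in Section 1.1 and Week 57 in Table 1-2. The dose-administration row of Table 1-2 is displaced in the text available and is not used.

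**Week labels.** Week = floor((day − 1)/7) + 1 reproduces the schedule: 29→5, 57→9, 85→13, 113→17, 176→26, 267→39, 358→52.

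**Can EOT be 14 days after the last dose?** Take the parenthesis as true for Day 358:

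- Last dose = 358 − 14 = Day 344, which is Week 50. Treatment is planned for up to 52 weeks.
- Safety contact = 344 + 30 to 344 + 37 = Days 374 to 381, Weeks 54 to 55. The plan says Week 56 or 57.
- Contact after EOT = 374 − 358 to 381 − 358 = 16 to 23 days. The plan says about 30.

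The parenthesis fails on all three.

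**Is EOT at about the last dose?**

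| Last dose | EOT (Day 358) minus last dose | Safety contact | Weeks |
|---|---|---|---|
| Day 344 | +14 | Days 374–381 | 54–55 |
| Day 358 | 0 | Days 388–395 | 56–57 |
| Day 364 | −6 | Days 394–401 | 57–58 |

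Only the last two rows fit the planned contact. EOT is thus nominally 0 days after the last dose, or 6 days before it if a full 364 days are dosed.

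**Size of the difference.** Let EOT fall k days after the last dose. The rule also covers the whole time on treatment, so the visit reading ends contraception max(k, 0) days after the last dose. The parenthesis ends it at 14 days. The difference is 14 − max(k, 0).

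- Last dose on the EOT day (k = 0): Day 358 against 358 + 14 = Day 372, a difference of 14 days. Across the ±10 window this is Days 348–368 against Days 362–382, still 14 days.
- Last dose on Day 364: k runs from 348 − 364 = −16 to 368 − 364 = +4, so the difference is 14 days, falling to 10 at the late edge of the window.
- Early stoppers: k is however long the EOT visit takes to arrange. The difference is under 14 days if the visit is delayed, and changes sign if it comes more than 14 days after stopping.

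**The case against.** The strongest reply is that the 14-day figure stands in the criterion itself. It is more specific and more protective than the visit label, and a site must ignore a stated interval to stop at day 0. Section 1.1 also gives a study duration of up to 54 weeks, which equals 52 + 2 and suggests that a two-week post-treatment end point was once intended. Both points make 14 days the likelier intention. Neither removes the conflict: the named event is still a scheduled visit at Week 52, and 54 weeks does not fit a contact at Week 56 or 57.

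Two of the supporting texts are weak. The SAP sentence defines EOS and not EOT, and it sits in a paragraph that appears to be carried over from the parent study, since it mentions a randomized dose and skipping EOS for those entering the extension. The clinic-day dosing instruction is general and does not say that a dose is given at EOT. The finding does not depend on either. The Week 52 timing, the two descriptions of the final contact and the early-stopper rule are enough.

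It is also fair that the 14-day gap holds only when EOT and the last dose coincide. The consequence is unproven as well: the PK and preclinical text is redacted, men need only 24 hours, the number of women affected is unknown, and the consent form was not available. Adverse events are followed for at least 30 days after the last dose. These points limit how serious the issue can be said to be. They do not make the rule clear.

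**Conclusion.** The criterion is wrong as written. Under the protocol's own schedule, the EOT visit and the point two weeks after the last dose cannot be the same date, and no other section says which one applies. For a completer whose last dose is on the EOT day, the two readings differ by 14 days. With dosing to Day 364 the difference is 10 to 14 days. For early stoppers it depends on when the visit is held.

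This rests on the final contact being about 30 days after both EOT and the last dose, as the protocol states. How many of the approximately 40 participants are women of child-bearing potential is not given, and the fetal risk in the interval cannot be assessed. No endpoint, analysis set or estimate changes. The point should be corrected because it is an operative participant-protection rule.

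**What to change.** In criterion 4, replace the end point with a fixed interval: contraception while taking study treatment and for 14 days after the last dose. If the Investigator's Brochure supports a different number of days, use that number. Remove the reference to the EOT visit, so that completers and early stoppers follow the same rule.

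The cost is one phrase in the protocol and the matching phrase in the consent form, if it appears there. No visit, test or data item is added. The one burden is up to 14 more days of contraception for women whose site would have stopped at the EOT visit.
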